#### 2.4.4 Secondary Analysis

For the two treatment groups, exact confidence intervals based on the binomial distribution will be calculated for the proportion of responders on the [REDACTED] and [REDACTED], as defined below.

[REDACTED]  
The proportion of responders based on [REDACTED]

[REDACTED] as assessed by the Blinded Evaluator at Weeks 16, 24, 32, 40, and 48 will be calculated and summarized by treatment group along with their two-sided 95% confidence intervals.

In addition, the change from baseline in [REDACTED] at Weeks 16, 24, 32, and 40 based on the Blinded Evaluator's assessment, for the right and left side of the face separately, will be calculated and summarized by treatment group.

Scores for the Treating Investigator at baseline and at each treatment visit will be listed only.

 GALDERMA	Title Statistical Analysis Plan 43USSA1705 - New label	Doc id MA-39345
--	--	---------------------------

The proportion of improved subjects based on [REDACTED] at Weeks 16, 24, 32, 40, and 48, will be calculated and summarized by treatment group along with their two-sided 95% confidence intervals. The proportions will be calculated separately for the subject's assessment and for the Treating Investigator's assessment. [REDACTED]

[REDACTED] In addition, the number and percent of subjects in each response category will also be summarized.

[REDACTED] scores will be summarized by treatment group at Week 24, 32, 40 and 48. The number and percent of subjects in each response category for each question will also be summarized.

### Subject Satisfaction

Answers on the subject satisfaction questionnaire will be summarized.

[REDACTED]

[REDACTED]

[REDACTED]

[REDACTED]

## 2.5 Safety Analysis

Safety endpoints will be summarized using descriptive statistics by treatment group based on the safety population using the Observed Cases (OC). There are no planned inferential statistical analyses of safety endpoints.

### 2.5.1 Treatment Administration, Procedural Anesthetics, and Injection Concomitant Procedures

The number and percentage of subjects receiving one administration of Sculptra, two administrations, three administrations, and four administrations will be summarized by treatment group.

Other treatment administration endpoints that will be summarized by treatment group and treatment session include (but are not limited to):

- Injection volume.
- Injection method.
- Depth of injection.

The number of subjects with any procedural anesthetics will be summarized by type and location. The number of subjects with any injection concomitant procedures will be summarized.

	
Title Statistical Analysis Plan 43USSA1705 - New label
	
Doc id MA-39345

--	--	-----------------------------------

Effective date: 2019-02-11 09:58

Effective

Version: 1.0

## 2.5.2 Adverse Events

A summary of all AEs (number and percentage of subjects with at least one event and number of events) will be provided, which will include:

- Subjects with at least one AE (in total as well as serious AEs).
- Subjects with at least one study product or injection procedure-related AE (in total as well as serious AEs).
- Subjects with at least one unrelated AE (in total as well as serious AEs).
- Subjects with at least one AE of special interest (in total as well as serious AEs).
- Number of subjects who did not have an AE.

As a sensitivity analysis, the above will be repeated using only randomized subjects.

Apart from the summary table described above, all other adverse event tables will be summarized in total and by treatment session: the first treatment session will include all AEs with a date of onset on or after the first treatment date but before the date of the second treatment or through the end of the trial if a subject receives only one treatment; the second treatment session will include all AEs with a date of onset on or after the second treatment date but before the date of the third treatment or through the end of the trial if a subject receives only two treatments, etc.

Study product or injection procedure-related AEs, as well as AEs unrelated to study product or injection procedure will be summarized by System Organ Class (SOC), Preferred Term (PT) and maximum intensity.

In addition, for study product or injection procedure-related AEs, the number of days to onset and the duration of event will be summarized by SOC and PT.

- Time to onset of an AE will be derived as the start date minus the date of the most recent treatment. If the start date is missing, it will be assumed that the AE started on the day of the most recent treatment.
- Duration of an AE will be derived as the stop date minus the start date + 1. If the start date is missing, it will be assumed that the AE started on the day of most recent treatment. Missing stop dates will not be imputed and therefore no duration will be calculated in these cases.

Actions taken for study product or injection procedure-related AEs will also be summarized.

Serious AEs, AEs of special interest, and AEs with late onset (i.e. AEs with onset > 21 days after most recent treatment) will be listed.

For subject counts, a subject will only be counted once per SOC and once per PT in cases where multiple events are reported for a subject within SOC or PT. For event counts, subjects with multiple events in a category will be counted for each event.

Further, separate summaries of the study product or injection procedure-related AEs, by treatment session and maximum intensity, will be created for each skin type and for each site, by SOC and PT.

 GALDERMA	Title Statistical Analysis Plan 43USSA1705 - New label	Doc id MA-39345
--	--	---------------------------

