Safety Objective and Endpoints	The objective is to evaluate the safety of Sculptra Aesthetic as a single regimen for correction of Nasolabial Fold (NLF) contour deficiencies after changes in reconstitution and injection procedures compared to the approved label. Safety endpoints 
 • Incidence, intensity, time to onset and duration of adverse events collected throughout the study period. • Incidence, intensity, time to onset and number of days of pre-defined expected post-treatment events collected using subject

Effective date: 2019-02-21 18:33

Effective

Version: 5.0

	
diaries for 28 days from each treatment.
 
 • [REDACTED]
Effectiveness Objectives and Endpoints	
The objective is to evaluate the effectiveness of Sculptra Aesthetic as a single regimen for correction of NLF contour deficiencies after changes in reconstitution and injection procedures compared to the approved label.
 
Primary effectiveness endpoint
 
Change from baseline on both sides of the face as assessed by the Blinded Evaluator using [REDACTED] at 48 Weeks after the first treatment session.
 
[REDACTED] [REDACTED] [REDACTED] [REDACTED] [REDACTED] [REDACTED] [REDACTED]

Study Design	
This is a prospective, randomized, evaluator-blinded, multicenter US study.

Subject Participation	
A subject may be involved in the study for approximately 52 weeks from screening to the final follow-up visit.

Enrollment	
Written informed consent will be obtained before any study related procedures is performed. Subjects will be screened for eligibility within 30 days prior to injection. The screening visit and baseline visit may be performed on the same day. Subsequent to screening, eligible subjects will be randomized in the study.
 
[REDACTED]
 
This study will include at least eight (8) subjects with Fitzpatrick Skin Type (FST) IV and at least eight (8) subjects with FST V-VI.

Effective date: 2019-02-21 18:33

Effective

Version: 5.0

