4.1 General outline

This is a 48-week, randomized, evaluator-blinded, parallel-group, multi-center, study to evaluate the safety and effectiveness of treatment with Sculptra Aesthetic for correction of NLF contour deficiencies after changes in reconstitution and injection procedures compared to the approved label.

Approximately 64 subjects requiring correction of NLFs will be enrolled and randomized in a 2:1 ratio to treatment with Sculptra Aesthetic reconstituted with 8 mL of SWFI (treatment group) or to Sculptra Aesthetic reconstituted with 5 mL of SWFI (reference group). In addition, eight (8) subjects with FST IV and eight (8) subjects with FST V-VI will be included but not randomized. These subjects will be treated with Sculptra Aesthetic reconstituted with 8 mL of SWFI. When these numbers of FST IV-VI have been treated, any additional FST IV-VI will be randomized in a 2:1 ratio (8 mL:5 mL).

Approximately 60 subjects will be treated with Sculptra Aesthetic reconstituted with 8 mL of SWFI and a reference group of approximately 20 subjects will be treated with Sculptra Aesthetic reconstituted with 5 mL of SWFI as according to the current label.

[REDACTED]

Investigator blinding will be accomplished by using a Treating Investigator to administer the

 GALDERMA	<small>Title</small> 43USSA1705 Sculptra Clinical Study Protocol	<small>Doc id</small> MA-37876
---	--	--

Effective date: 2019-02-21 18:33

treatments and a Blinded Evaluator, to whom randomization and treatment are concealed, to conduct the blinded assessments. In addition, the Blinded Evaluator should not be allowed to retrieve study supplies or be present during the opening of the study supplies or injection procedure. All documents with information regarding study products and randomization assignment should be kept in a separate binder not available to the blinded evaluator. Safety assessments will be performed by non-blinded personnel.

Eligible subjects randomized to receive treatment will be injected by the Treating Investigator at Day 1. The method of injection is at the discretion of the treating Investigator according to Sections 2.2 and 6.6.

Sufficient amount of product should be injected to achieve optimal correction of the NLFs, in the opinion of the Treating Investigator and subject.

Information will be collected about treatment procedure (e.g. injection technique, depth, injection volume, needle sizes, and anesthesia used).

*Effective*

Version: 5.0

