#### 1.1.1 Study Design

This is a randomized, multicenter, evaluator-blinded study to evaluate the safety and effectiveness of Sculptra Aesthetic for correction of nasolabial folds.

Eligible subjects will be treated with a single regimen of Sculptra Aesthetic on both sides of the face, starting at the baseline visit. A single regimen consists of up to 4 injection sessions with 4-week (+7 days) intervals. Subjects will be treated with either Sculptra Aesthetic reconstituted with 8 mL of sterile water for injection (SWFI) or with Sculptra Aesthetic reconstituted with 5 mL of SWFI.

Subjects will be randomized (2:1) to either treatment with Sculptra Aesthetic reconstituted with 8 mL of SWFI or to treatment with Sculptra Aesthetic reconstituted with 5 mL of SWFI.

At least eight (8) subjects will be Fitzpatrick skin type (FST) IV and at least eight (8) subjects will be FST V-VI.

Clinical study participation for each subject is up to approximately 52 weeks from screening to the final follow-up visit.

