## 1.4 Effectiveness Endpoints

### 1.4.1 Primary Effectiveness Endpoint

Change from baseline on both sides of the face as assessed by the Blinded Evaluator using [REDACTED] at 48 Weeks after the first treatment session.

	
Title Statistical Analysis Plan 43USSA1705 - New label
	
Doc id MA-39345

--	--	-----------------------------------

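### AE tables by treatment session compare windows of 4–5 weeks with last-session windows of 33–48 weeks, so unrelated and delayed-onset AEs can look more frequent in later sessions without any session effect

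*SAP*

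**What the plan says.** SAP 1.1.1 sets the treatment course: "A single regimen consists of up to 4 injection sessions with 4-week (+7 days) intervals". The number of sessions is therefore one to four and varies between subjects. SAP 2.5.1 plans to tabulate it by treatment group.

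SAP 2.5.2 first describes an overall AE summary that is not split by session. Every other AE table is presented both overall and by session. The first session's window takes AEs with onset "before the date of the second treatment or through the end of the trial if a subject receives only one treatment". For the second session it runs to just "before the date of the third treatment or through the end of the trial if a subject receives only two treatments, etc". The same section adds, for each skin type and each site, "separate summaries of the study product or injection procedure-related AEs, by treatment session and maximum intensity".

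For AEs related to the product or the injection, days from the most recent treatment to onset are summarized. AEs starting more than 21 days after the most recent treatment are listed. SAP 2.5 plans no inferential analysis of safety. The visible text gives no subject-time, common risk window or breakdown by number of sessions for these tables, and it does not state the denominator of a session column.

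**The concern.** A table with one column per session invites the reader to compare the columns and ask whether risk changes as injections accumulate. That reading is fair only if the columns cover similar follow-up. Here a session's window is short if another session follows and long if none does. The columns for sessions 1 to 3 can mix short and long windows, and the session 4 column holds only long ones, apart from early withdrawals.

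Events that accrue with time, such as unrelated illness or late reactions, will collect in whichever session came last. A rise towards session 4 could then be read as cumulative risk. If one dilution tends to need fewer sessions, its long windows sit in earlier columns, and the two arms differ within a column for the same reason. The skin-type and site tables of related AEs inherit this for delayed-onset events, in smaller groups. With no inferential safety analysis, and an acceptable safety profile among the success criteria in SAP 2.1, readers will rely on these descriptive tables.

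**Working it through.** **1. When the trial ends for a subject.** The primary endpoint is assessed "at 48 Weeks after the first treatment session" (SAP 1.4.1), and Protocol 4.1 begins "This is a 48-week, randomized, evaluator-blinded, parallel-group, multi-center, study". The Protocol synopsis allows a screening period: "Subjects will be screened for eligibility within 30 days prior to injection". Hence 48 + 30/7 = 52.3 weeks. This reproduces the stated participation of "approximately 52 weeks from screening to the final follow-up visit" (SAP 1.1.1), so the end of the trial is taken as Week 48 after first treatment.

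**2. Window lengths.** The planned interval d is 28–35 days, or 4–5 weeks. A session followed by another has window d. The last of k sessions has window 48 − d(k − 1). The ratio runs from (shortest last window)/5 to (longest last window)/4.

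| Sessions received | Last window (weeks) | Ratio to a 4–5 week window |
|---|---|---|
| 1 | 48 | 9.6–12 |
| 2 | 43–44 | 8.6–11 |
| 3 | 38–40 | 7.6–10 |
| 4 | 33–36 | 6.6–9 |

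**3. Effect for one subject with four sessions.** The documents give no AE rate, so a constant rate λ per subject-week is assumed over a range. The chance of at least one AE in a window of w weeks is 1 − exp(−λw).

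| Assumed λ | Sessions 1–3 (4 weeks each) | Session 4 (36 weeks) |
|---|---|---|
| 0.5% | 2.0% | 16.5% |
| 1% | 3.9% | 30.2% |
| 2% | 7.7% | 51.3% |

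**4. Effect on a whole table.** Assume that 10/20/30/40% of subjects receive 1/2/3/4 sessions, that intervals are 4 weeks, and that each column's denominator is the subjects who received that session. Mean windows are then:
- session 1: 0.1×48 + 0.9×4 = 8.4 weeks
- session 2: (0.2×44 + 0.7×4)/0.9 = 12.9 weeks
- session 3: (0.3×40 + 0.4×4)/0.7 = 19.4 weeks
- session 4: 36.0 weeks

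At λ = 1% the column percentages are 7.3%, 11.0%, 16.4% and 30.2%, although every session carries the same risk.

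**5. Acute events.** Give each session an assumed 20% risk of an event that starts within the first 4 weeks, with no background rate. Every column shows 20.0%, because every window covers those weeks. Adding the 1% background under the same mix gives 25.9%, 28.8%, 33.1% and 44.2%. The gradient comes from the background alone.

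**6. After splitting at 35 days.** The last session's column covers 5 weeks and the other windows cover 4–5. At λ = 1% a window then has a chance between 3.9% (4 weeks) and 4.9% (5 weeks), so the gradient almost disappears.

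**The case against.** The case for leaving the tables alone has real substance. Attributing an AE to the most recent treatment is a clear and reproducible rule. Injection reactions mostly matter in the first weeks, and every window that another session closes lasts at least about 28 days. The overall AE summary, repeated in randomized subjects only, and the in-total presentation of every other table compare the dilutions over the same planned follow-up. Onset time is summarized for related AEs, late-onset AEs are listed, and diary events already have a common 28-day window. Table layouts are in a companion document (SAP 2.1.2), so denominators and footnotes cannot be judged. The SAP numbering also passes from 2.5.2 to 2.5.4, so a safety subsection may have been removed from the public copy.

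Most of this stands, and it rules out three stronger readings that a reader might infer:
- **That the session columns reflect only follow-up time.** Step 5 shows that this is wrong for acute injection events.
- **That AEs will be 7–9 times more frequent in the last session.** That needs a constant rate over 48 weeks, which the documents do not give. It suits injection-related events poorly, and the skin-type and site tables contain only related AEs.
- **That the dilutions are not comparable.** That holds only for session columns, and only if the number of sessions differs by arm. Protocol 4.1 leaves the amount injected to the Treating Investigator and the subject, and Protocol 4.4.2 leaves that investigator unblinded, so a difference is possible. Nothing shows that it will occur, and SAP 2.5.1 would reveal it.

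What the objection does not remove is narrower. Unrelated AEs have no onset summary, late-onset AEs are listed rather than tabulated, and comparison of sessions within an arm stays distorted for both kinds of event even if the arms receive equal numbers of sessions.

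**Conclusion.** The point holds as a minor one about presentation. Session windows differ 6.6- to 12-fold by construction: 4–5 weeks for a session followed by another, against 33–48 weeks for the last one received. By-session figures for unrelated and delayed-onset AEs can therefore rise across sessions with no session effect, and can differ between dilutions if session numbers do.

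The window lengths follow from the documents, given the planned intervals and no early withdrawal, which would shorten some last windows. The percentages rest on assumed rates and an assumed mix of session numbers, and only illustrate the mechanism. Acute injection events, the in-total columns and the overall AE summary are not affected, and no test or success threshold depends on the session columns.

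**What to change.** Keep the totals and the assignment to the most recent treatment, and add one of the following to SAP 2.5.2 and the table layouts.

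- **Split the last window.** Move events that start more than 35 days after the last treatment received into a separate long-term follow-up column. The cut matches the longest planned interval. A 28-day cut, as in the diary, would leave events on days 29–35 between two sessions to be labelled as follow-up while treatment was still under way.
- **Show exposure.** For each session column, give the number of subjects treated, the subject-time at risk, and events per subject-time beside the counts. Rates should not replace counts. An acute risk of 20% spread over the window is 20/4 = 5.0% per week in a 4-week window but 20/36 = 0.56% per week in a 36-week one, so rates alone would make the last session look safer for acute events.

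The split is easier to read for both kinds of event. Either option uses dates already collected, and the SAP already defines time from the most recent treatment to onset. The cost is a sentence or two in the SAP, a derived variable in the AE dataset, and one more line or column per table.

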4.4.2 Blinding

Blinding will be accomplished by using a Treating Investigator to administer the treatments and a Blinded Evaluator, to whom randomization and treatment are concealed, to conduct the blinded assessments. The Treating Investigator will not be blinded. The Blinded Evaluator is not allowed to discuss treatments with the Treating Investigator or subjects. No study related documents that contain information regarding the treatment of subjects should be available to the Blinded Evaluator. Safety assessments will be performed by non-blinded personnel who are qualified by training and experience.

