7.7.3.2 Causal relationship and seriousness

Each AE, serious as well as non-serious, shall be assessed by the Investigator for causal relationship with the study product and its use (the injection procedure) and for seriousness (Yes or No) of the event.

A two-point scale (Yes or No response) shall be used for the causality assessments. The Investigators shall be asked to indicate a response to each of the following questions in the eCRF:

- “Do you consider that there is a reasonable possibility that the event may have been caused by the study product?”, and
- “Do you consider that there is a reasonable possibility that the event may have been caused by the study product injection procedure?”

 Title **43USSA1705 Sculptra Clinical Study Protocol** Doc id **MA-37876**

Effective date: 2019-02-21 18:33

Effective

Version: 5.0

If any of these questions is answered “Yes”, the AE is considered related.

Each AE will also be assessed for causal relationship and seriousness by the Sponsor, in order to fulfil regulatory requirements.

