10.6 Safety analysis

Number and percentage of subjects reporting each pre-defined, expected, post-treatment symptoms, as collected in the 28-day diary, will be presented in total and by maximum severity.

All AEs will be coded according to MedDRA and summarized by system organ class (SOC), preferred term (PT) and treatment.

 GALDERMA	Title 43USSA1705 Sculptra Clinical Study Protocol	Doc id MA-37876
--	---	---------------------------

Effective date: 2019-02-21 18:33

Effective

Version: 5.0

Effective date:

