#### 1.6 Safety Endpoints

Safety endpoints include:

- Incidence, intensity, time to onset, and duration of adverse events collected throughout the study period.
- Incidence, intensity, time to onset and number of days of pre-defined expected post-treatment events collected using subject diaries for 28 days from each treatment.
- [REDACTED]  
[REDACTED]

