### 2.8 Changes in the Analysis Planned in the Protocol

There have been no substantial changes from the statistical methods described in the protocol.

 GALDERMA	<small>Title</small> Statistical Analysis Plan 43USSA1705 - New label	<small>Doc id</small> MA-39345
---	---	--

2019-02-11 09:58

Effective date:

*Effective*

Version: 1.0

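### SAP 2.5.2, as visible, has no all-AE table by SOC, PT and treatment group, and it limits time to onset and duration to AEs that unblinded staff judge related.

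*SAP*

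**What the plan says.** SAP 1.6 defines the first safety endpoint as "Incidence, intensity, time to onset, and duration of adverse events collected throughout the study period". Protocol 3.1 defines it in the same way, and neither limits it by cause. Protocol 10.6 (version 5.0) adds: "All AEs will be coded according to MedDRA and summarized by system organ class (SOC), preferred term (PT) and treatment".

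SAP 2.5.2 starts with an overall summary: any AE, related AE, unrelated AE and AE of special interest, each in total and for serious events. By event type it then plans one SOC/PT/maximum-intensity summary for related AEs and another for unrelated AEs. On timing it says that "for study product or injection procedure-related AEs, the number of days to onset and the duration of event will be summarized". Actions taken, and the skin-type and site tables, are also for related AEs only. SAP 2.5 states that safety summaries are by treatment group and descriptive.

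Relatedness comes from two yes/no questions answered by the Investigator, and one yes is enough (Protocol 7.7.3.2). On blinding, Protocol 4.4.2 says "The Treating Investigator will not be blinded" and "Safety assessments will be performed by non-blinded personnel who are qualified by training and experience". There is a second assessment: "Each AE will also be assessed for causal relationship and seriousness by the Sponsor, in order to fulfil regulatory requirements". SAP 2.6 notes that the Sponsor is not blinded.

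SAP 2.1 gives the SAP precedence over the statistical sections of the protocol. SAP 1.1 says that the SAP was written for protocol version 3.0.

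**The concern.** The trial compares the safety of a changed reconstitution and injection procedure with the labelled one. SAP 2.7 shows how much weight safety carries: effectiveness needed 26 subjects in the 8 mL group, and the group was raised to 60 to give enough safety data.

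In an evaluator-blinded trial, the causality call is one of the judgements that the blind does not protect. If staff attribute events differently in the two groups, the related-AE table shows a difference that is partly attribution. The usual check is an all-causality table by event type, which does not depend on that call. The visible SAP 2.5.2 does not plan one. For onset and duration the gap is wider, because an AE judged unrelated is left out of those summaries altogether, although the endpoint includes it.

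**Working it through.** No figure in the plan is at issue, so the check is mainly of which outputs are planned.

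**1. Outputs in the visible SAP**

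| Output | By event type | Depends on relatedness |
|---|---|---|
| Any-AE row of the overall summary (2.5.2) | No | No |
| AESI row of the overall summary (2.5.2) | One group of events | No |
| SOC/PT/maximum intensity (2.5.2) | Yes | Yes: related and unrelated apart |
| Onset and duration (2.5.2) | Yes | Yes: related only |
| Skin-type and site tables (2.5.2) | Yes | Yes: related only |
| Diary symptoms (2.5.4) | Yes: pre-defined, 28 days per treatment | No |
| Nodules and papules (2.5.5) | Yes | None stated |
| Listings (2.1.2, 2.5.2) | Subject level | No |

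Against endpoint 1.6, incidence and intensity of AEs by type appear only in split form. Onset and duration are missing for AEs judged unrelated.

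**2. Who decides relatedness**

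The treating investigator, the safety assessors and the Sponsor all know the treatment. The documents describe no blinded causality assessor.

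**3. Group sizes**

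Protocol 4.1 randomizes about 64 subjects 2:1 and adds 16 non-randomized subjects to the 8 mL group. That gives 64 × 2/3 + 16 = 58.7 and 64/3 = 21.3, consistent with the stated 60 and 20.

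**4. Why subject counts do not add**

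For one PT, let R subjects have a related event, U an unrelated event and B both. The number with the PT is R + U − B, where B can be anything from 0 to the smaller of R and U. With assumed R = 12 and U = 9 out of 60, the total is 21 − B with B from 0 to 9. That is 12 to 21 subjects, or 12/60 = 20% to 21/60 = 35%. Event counts have no overlap term and can be added.

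**5. What attribution can do (assumed counts and rates)**

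- *Equal rates made to look unequal.* Suppose that 6/60 and 2/20 subjects have the same event, 10% in each group. If two 8 mL cases are called unrelated, the related table shows 4/60 = 6.7% against 2/20 = 10%, and the unrelated table shows 2/60 = 3.3% against 0. Onset and duration then rest on 4 of the 6 cases in the 8 mL group and on both cases in the reference group.
- *Unequal rates made to look equal.* Suppose that all-cause rates are 30% (8 mL) and 20% (5 mL), and that 40% and 60% of affected subjects have the event called related. The related table shows 0.30 × 0.40 = 12% against 0.20 × 0.60 = 12%.
- *One subject.* Moving one subject changes a related-AE rate by 1/20 = 5.0 points in the reference group and 1/60 = 1.7 points in the 8 mL group.

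**The case against.** The strongest reply is that little is lost. Related and unrelated AEs together make up all AEs, and both are tabulated by SOC, PT and intensity. SAP 2.1 allows its analyses to be more explicit than the protocol's, and a two-way split can be read in that way. In the first example above, the two reattributed cases appear under the same PT in the unrelated table, where a reader can see the shift and rebuild the total. Subject counts fail to add only when one subject has both a related and an unrelated event of the same PT, and nothing in the documents suggests that this is common. No safety test is planned, so no test result changes. Days since the last injection may also tell little about an event judged unrelated.

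Most of this stands, and it limits the point. It does not remove it: a total that the reader must rebuild from listings is not a planned table, and endpoint 1.6 is not restricted to related events.

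Two stronger readings should be resisted.

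- A reader might infer that no all-cause comparison by event type remains. The documents do not support that. Diary symptoms, nodules and papules, the AESI row and the listings are not split by causality, and event counts per PT can be added. These outputs only partly fill the gap: the diary, for example, covers pre-defined symptoms for 28 days per treatment, while the AE endpoint runs throughout the study.
- A reader might infer that SAP 2.8 is untrue where it says "There have been no substantial changes from the statistical methods described in the protocol". That statement refers to protocol version 3.0, dated 15 October 2018, which is not available here. The text of 10.6 cited above is from version 5.0, effective ten days after the SAP (21 against 11 February 2019).

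The visible text also has limits. SAP numbering goes from 2.5.2 to 2.5.4, parts of Protocol 10.6 are blank, and table formats are in a companion document. A further AE table in those places cannot be excluded.

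**Conclusion.** The point holds in limited form. On the visible text, SAP 2.5.2 lacks the all-AE table by SOC, PT and treatment that the current protocol states, and it gives onset and duration only for AEs judged related. The onset and duration gap lies within the SAP itself (2.5.2 against 1.6), so it does not depend on the protocol version.

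The consequence is that by-type subject rates for AEs, and all onset and duration summaries, depend on a judgement made without blinding. How far they would shift cannot be derived from the documents: the counts and attribution shares in steps 4 and 5 are assumed and show only what is possible. The 5.0 and 1.7 points per subject hold for any table in groups of this size and are not evidence that attribution will differ. Neither the primary effectiveness result nor the sample size is affected. The change is worth making because it is cheap and safety data are a main output of this trial.

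**What to change.** In SAP 2.5.2:

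- Add an all-causality AE table by SOC and PT, by treatment group, counting each subject once per PT whatever the attribution. Maximum intensity can be included to match the existing tables; the visible AE text of Protocol 10.6 does not itself ask for it.
- Summarise time to onset and duration for all AEs.
- Keep the related-only tables as supportive.

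Bring the SAP into line with the current protocol version and update SAP 1.1, which cites version 3.0. If the sponsor prefers to keep onset and duration for related AEs only, that should be reconciled with endpoint 1.6 and recorded in SAP 2.8.

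The cost is a short SAP amendment and a few table runs on data already collected, with no change to sample size. The downside is slightly longer output that includes unrelated events.
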